Aim # 2: Determine critical neuromechanical factors influencing response to targeted or non-targeted therapy

Hypothesis: Response to targeted therapy will be associated with recovery of more normal UE movement and muscle activity patterns. **Approach:** Our measurement framework successfully allows us to target therapy. However detailed neuromechanical analysis is critical for documenting the baseline status of motor control process in order to quantify treatment-related changes in these processes. Multiple regression models will be used to determine the influence of pre- to post-intervention changes in neuromechanical factors and UE motor impairment as measured by the Rasch FMA-UE change score. This knowledge will enable further refinements of existing treatments and facilitate development of new treatments to target underlying factors.

Aim #3: Determine critical predictors of the time-course of response to rehabilitation.

Hypothesis: People with stroke have different patterns of recovery; key neuromechanical variables predict these patterns. Approach: Growth mixture modeling (GMM) will be applied to longitudinal Rasch FMA-UE measures. GMM separates a sample into subgroups of people showing similar recovery patterns, and specifies neuromechanical factors predicting these patterns. Using GMM within our measurement framework is a highly innovative method to identify distinct groups with similar recovery trajectories and describe each group's behavior in terms of FMA-UE items that can/cannot be performed over the time course of treatment.

B. BACKGROUND AND SIGNIFICANCE

Each year over 795,000 individuals in the USA have a stroke.¹ Stroke causes brain cell damage or cell death which then leads to altered patterns of connectivity in cortical and sub-cortical neural networks supporting movement.² Over 75% of stroke survivors experience some degree of upper extremity (UE) paralysis.³ Unfortunately, UE motor function rarely recovers completely; 85% of those who survive stroke report residual arm/hand motor impairment severe enough to interfere with performance of daily tasks at 4 years post-stroke.⁴

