We will follow implementation of the therapy as per the published manual, online videos and available implementation guidelines. In addition, the PI recently attended an 8 hour workshop to develop competence in providing the therapy. We argue that Functional Upper Extremity Training⁷⁷ is not a "targeted" intervention according to our definition. That is, the approach does not specifically target a person-ability level because there will be no guidance from a measurement framework from which to choose appropriate tasks to ameliorate underlying specific deficits.

Specific to Aim 1: Compare the effects of targeted rehabilitation versus *non*-targeted rehabilitation on UE motor function.

Hypothesis: Targeted intervention will result in a greater pre- to post-intervention reduction of UE motor impairment when compared to *non*-targeted intervention.

Rationale: The Rasch-based FMA-UE classification defines levels of UE motor ability by describing UE movement tasks (FMA-UE items) which patients in each level can easily perform, cannot perform (too hard), and are well-matched to ability level. This information is the basis for designing task-practice sessions to specifically target the patient movement abilities. Because treatment is likely to induce changes in these variables, it is reasonable to expect changes in participants' Rasch FMA-UE measure.

Approach: *Dependent Variable:* The dependent variable will be change in UE motor impairment as measured by the percent change in the Rasch FMA-UE occurring from pre- to post-intervention. The Rasch FMA-UE percent change will be calculated as Post minus Pre divided by Pre.

Independent Variables: The independent variable is Group. The independent variable has two levels; targeted-therapy and non-targeted therapy.

Data Analysis: ANOVA will be used to compare the mean values of the Rasch FMA-UE change scores for each targeted vs. non-targeted treatment group across each impairment level (mild, moderate, severe). We will correct for multiple comparisons, therefore, significance for all comparisons will be alpha = 0.05/3 = 0.02.

Specific to Aim 2: Determine critical neuromechanical factors that influence response to targeted or *non*-targeted therapy

Hypothesis: Response to targeted therapy will be associated with recovery of "normal" UE movement and muscle activity patterns.

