Rationale: Very little is known about the neural and biomechanical mechanisms contributing to post-stroke UE motor impairment. Identification of the critical kinematic and neural aspects of reach contributing to changes in UE motor impairment occurring with therapy will permit refinement of existing and development of new interventions specifically targeted at improving these motor control process.

Approach: As described in the procedures above, we will collect kinematic and electromyographic (EMG) data to provide information about motor control strategies (kinematic) neural influences on motor output (EMG) responding to therapy.

Dependent Variable: The dependent variable will be change in UE motor impairment as measured by the percent change in the Rasch FMA-UE occurring from pre- to post-intervention as calculated above.

Independent Variables: We hypothesize that 3 independent variables will explain changes in UE motor impairment expected to occur with rehabilitation. These variables will be measured as the percent change in each variable occurring from pre- to post-intervention (post minus pre divided by pre). The variables were chosen because they are reasonable measures of "normal" movement based on the literature, motor control theory and clinical interpretation. Two kinematic variables (trunk movements, elbow extension range of motion) provide information about the strategy utilized to execute the movement. Trunk movement will be calculated as the cumulative distance a marker placed at T-10 travels during the reach. Voluntary elbow extension is calculated as difference between elbow joint angle at start and the joint angle at touch. One EMG variables (Biceps-Triceps co-

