contraction index) provide information regarding neural influences on motor output. The mean amplitude obtained during 5 sec. resting EMG activity will be used as baseline EMG values. For each trial, "time-to-EMG" is calculated as the difference between muscle onset and movement onset. Muscle onset is defined as a rise in EMG exceeding 4 standard deviations above resting EMG. Muscle offset is defined as a decrease in EMG below this value. Movement onset is defined as the time-point when velocity of the wrist marker exceeded 5% peak velocity. Positive time-to-EMG values indicate anticipatory muscle activation (occurred prior to movement onset); negative time-to-EMG values indicate delayed muscle activation (occurred after movement onset). The EMG activity occurring between onset and offset is defined as burst duration. A co-contraction index variable will be defined as Biceps Burst Duration divided by Triceps Burst Duration so that a value equal to 1 reflects simultaneous activity of the agonist and antagonist.

Data analysis: Two multiple regression models will examine the relationships between the dependent and independent variables. One regression model will include variables from all patients involved in targeted-therapy (i.e., pooled data from across UE impairment levels). The second model will include variables from all patients involved in non-targeted therapy.

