We will first investigate assumptions of normality for all variables via visual inspection of probability plots and statistically verified with the Kolmogorov-Smirnov f test. If the data are not normally distributed, they will be logarithmically transformed. Although we expect that all variables will be associated with the FMA-UE person-measure, we do not expect that a simple linear trend will best describe this relationship. It is likely that the response variables have a different impact on the FMA-UE person-measure according the level of UE motor impairment. Thus it is likely that a polynomial relationship exists between the response variables and the dependent variable. To determine whether a linear or polynomial regression model best fits our data we will first cross-plot each response variable against the dependent variable. Visual inspection of the scatterplot will help to facilitate the appropriate model and identify outliers which may affect the model. Outlier data points beyond 3 standard deviations of the mean value of that variable will be inspected to determine if the data was entered correctly. If not, the data point will be considered an aberrant rating and dropped from analysis. When it is determined that a quadratic trend likely best fits the data, we will transform the variable to its quadratic term via its unstandardized residual to compensate for multicollinearity. We will then apply a general linear model regression procedure to the data using SAS. A forced-entry procedure will be employed in which all variables will be examined for each model. Adjusted R-square values, p-values and 95 percent confidence intervals will be calculated.

We will test significance of the coefficient of determination (adjusted R-square value) for each response variable. The null hypothesis tested is that there is no significant association between each response variable and the dependent variable, meaning that the response variable does not contribute to UE motor ability (FMA-UE person measure). The alternative hypothesis is that the association is significant meaning that the response variable is associated with UE motor ability (FMA-UE person measure). We will reject the null hypothesis if $p < 0.05$ which will lead to the conclusion that the response variable does not contribute to the FMA-UE score at a 0.05 significance level.

Specific to Aim 3: Determine critical predictors of the time-course of response to targeted rehabilitation.

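### Dividing Rasch FMA-UE logit change by baseline reverses the sign of improvement for every severe patient: unavoidable in Aim 2 as written, and in conflict with the SAP for Aim 1

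*Protocol*

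**What the plan says.** **Aim 1, protocol** (Research Design and Methods, Specific to Aim 1). The outcome is percent change from before to after treatment: "The Rasch FMA-UE percent change will be calculated as Post minus Pre divided by Pre". Targeted and non-targeted groups are compared by ANOVA across the three impairment levels at 0.05/3. The text does not say whether this means three separate tests or one ANOVA with a common error term.

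**Aim 1, SAP** (same version number and date). The outcome is the person measure itself at Pre, Mid and Post, in a mixed-model ANOVA that tests the Treatment main effect at 0.05. There is no division by baseline. The SAP covers no other aim.

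**Aim 2, protocol** (Specific to Aim 2). The outcome is the "percent change in the Rasch FMA-UE occurring from pre- to post-intervention as calculated above". "One regression model will include variables from all patients involved in targeted-therapy (i.e., pooled data from across UE impairment levels"; a second model does the same for the non-targeted arm. On entry of predictors: "A forced-entry procedure will be employed in which all variables will be examined for each model". On non-normal data: "If the data are not normally distributed, they will be logarithmically transformed". Points beyond 3 SD "will be inspected to determine if the data was entered correctly", and are dropped only if they were not.

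Two other Aim 2 phrases name the outcome without a formula. Specific Aims refers to "UE motor impairment as measured by the Rasch FMA-UE change score", and the hypothesis-test paragraph has "meaning that the response variable does not contribute to UE motor ability (FMA-UE person measure".

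**Scale.** Ratings are converted to logits with anchored item difficulties. Severe means below -0.22 logits in Table 4, while the text with Table 3 puts the severe/moderate threshold at -0.12. The moderate/mild threshold is 2.44 in both places. No shift to a positive scale, absolute-value denominator or rule for baselines near zero is given.

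**The concern.** Percent change is meaningful only on a scale with a true zero and positive values. Logits have neither. With a negative denominator an improvement scores negative, and a bigger improvement scores more negative. With a denominator near zero the score is dominated by how close the baseline happens to lie to an arbitrary origin.

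In Aim 2, patients whose scores mean opposite things enter one regression, so it is very unlikely to show whether changes in trunk movement, elbow extension and co-contraction track recovery. In Aim 1, if the protocol definition is followed, a better targeted therapy scores below control in the severe level, and the other levels are damaged in ways that depend on the error term. If the SAP definition is followed, this does not arise for Aim 1.

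**Working it through.** **1. The plan's own sizing is in logits.** Pilot post-training values are 2.30 (SD 1.00) and 1.42 (SD 0.45). So d = 0.88 / sqrt((1.00² + 0.45²)/2) = 0.88/0.775 = 1.135, against the stated 1.13. At two-sided 0.05, an exact t calculation gives 18 per group (power 0.909), and 18 × 6 = 108. Both figures reproduce, and neither uses percent change.

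**2. Zero is a calibration origin.** The 17 positive difficulties in Table 2 sum to 12.27 and the 13 negative ones to -12.27, so the mean of all 30 is 0.00. Severe baselines are all negative under either cut, and moderate baselines span zero under either cut.

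**3. The formula on the pilot gains.** Targeted: 2.30 - 0.90 = 1.40. Non-targeted: 1.42 - 0.89 = 0.53. Score = gain/Pre.

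| Pre (logits) | Gain 1.40 | Gain 0.53 |
|---|---|---|
| -3.0 | -47% | -18% |
| -1.0 | -140% | -53% |
| -0.22 | -636% | -241% |
| +0.1 | +1400% | +530% |
| +3.0 | +47% | +18% |

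Below zero, the larger gain always has the lower score. This step needs no assumption beyond the documents' own cuts.

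**4. How far this reaches (illustrative).** The documents give no baseline distribution by level and no SD of gain. Assumed: uniform baselines (severe -2.5 to the cut, moderate from the cut to 2.44, mild 2.44 to 4), gain independent of baseline, gain SD 0.5 to 1.0, 18 per arm per level, and both cuts. The share of improvers coded as worse is then (1 + 0.22/2.66)/3 = 36% or (1 + 0.12/2.56)/3 = 35%.

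**5. Aim 2** (18 × 3 = 54 per arm, three predictors by forced entry, two-sided 0.05, 4,000 replicates).
- Each predictor assumed to correlate 0.4 with logit gain: detected in the right direction in about 96% of trials on logit change and 2-4% on percent change. Median adjusted R-square is about 0.47 against -0.01.
- One real predictor at r = 0.5: 97-98% against 2.5-5%.
- Percent change stays at 2.6-3.5% after removing points beyond 3 SD, adding quadratic terms, or cutting the severe gain to one third.
- With every baseline at least 0.5 logits from zero it is still only 4-8%, so sign reversal alone is enough.

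The plan's safeguards do not help. Correctly entered extreme values stay in, and the log of a negative change score is undefined.

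**6. Aim 1, only if the protocol definition governs** (pilot gains, alpha 0.0167, 20,000 replicates). The targeted mean falls below the non-targeted mean in the severe level in 94-99.6% of trials (81-97% at half the gains, 73-90% at one third).

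| Significant result | Percent change, separate t-tests | Percent change, pooled-error ANOVA | Logit change |
|---|---|---|---|
| Severe, for targeted | 0.1% or less | 0.1% or less | 54-99.7% |
| Severe, for non-targeted | 18-57% | 2-6% | – |
| Moderate, power | 1-4% | 14-20% | 54-99.7% |
| Mild, power | 52-99% | about 0% | 54-99.7% |

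Different assumptions change the rates but not the direction. With severe baselines uniform from -3 to -0.22, gain SD 0.25 to 1.0 and separate tests at 0.05, 40-85% of trials are significant in the severe level, all against targeted therapy. With moderate baselines drawn from the pilot means and SDs, moderate power is 7-12% on percent change against 72-100% on logit change.

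**7. The SAP alternative.** Its Treatment main effect averages in Pre, when the arms cannot yet differ by treatment. With 54 per arm, alpha 0.05, the -0.22 cut and an assumed mid-treatment gain of half the final one, power is 79-90% at pilot gains and 28-37% at half. The Pre-to-Post contrast has 99-100% and 61-99%.

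**The case against.** **The SAP is the analysis document, and it does not divide by baseline.** The sample size is also in logits, and the protocol's own Aim 1 analysis sentence speaks of change scores. This stands to the extent that Aim 1 is an unreconciled conflict, not a demonstrated reversal. It does not remove the conflict, since no precedence is stated.

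**Aim 2 has competing wording.** Change score would ordinarily be read as Post minus Pre. But those phrases carry no formula, and the Aim 2 outcome definition points explicitly to the Aim 1 calculation. Aim 2 is explanatory, not the treatment comparison; it is nevertheless one of three stated aims.

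**The simulated rates are not forecasts.** This stands. The Aim 2 model uses generic predictors rather than percent changes, and does not simulate the log-transform branch. Three predictors at r = 0.4 is a generous assumption, so 96% is not the expected power after the fix. The pilot enrolled only moderate patients, yet its gains are applied to mild baselines up to 4 logits, although the hardest item sits at 1.67. No ceiling was modelled, so the mild-level rates are the weakest.

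Treating Rasch measures as discrete, or using pilot-based moderate baselines for Aim 1, does not rescue the formula. The severe wrong-sign rate stays at 93-99.6% at pilot gains, and with discrete measures Aim 2 detection stays at 3-4%.

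**The SAP main effect and the elbow-extension denominator are separate defects.** True. They appear here only because the repair touches them.

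**Conclusion.** The concern holds, and the plan must be changed. The sign reversal for every severe patient, and for moderate patients below zero, follows from the formula and the documents' own thresholds, as does the blow-up near zero. It holds under either severe/moderate cut.

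For Aim 2 it applies to the only formula given, and nothing else in the plan cures it. On the stated assumptions, detection of a real association falls from about 96% to 2-4%. For Aim 1 it is conditional. If the protocol definition is used, the severe comparison points the wrong way in 94-99.6% of simulated trials at pilot gains; if the SAP definition is used, it does not arise. The direction is certain. The rates depend on assumed baselines, gain SDs and correlations.

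**What to change.** Delete division by Pre for the Rasch FMA-UE in both aims.

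- **Aim 2.** Define the outcome as Post minus Pre in logits, preferably with Pre as a covariate. Do not log-transform signed change scores. Use absolute change for elbow extension too: it is a difference of two angles, and Preliminary Studies 3e illustrates a severe patient with almost none, so its baseline can be near zero. Trunk distance and the co-contraction ratio are not signed quantities, so this argument gives no reason to change them. How small the burst-duration denominator can get was not examined.
- **Aim 1.** State one logit-scale outcome, one primary analysis and one alpha, identically in protocol and SAP. If levels are tested separately, say whether the error term is pooled. If the SAP mixed model is kept, test the Treatment-by-Time contrast from Pre to Post, or baseline-adjusted Post, instead of the main effect that averages in Pre.
- **Thresholds.** The -0.12 and -0.22 values must be reconciled separately. This point does not depend on which is used.

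The cost is wording in two documents, with no new data. The change should be made before outcome data are analysed, so that the replacement outcome is not chosen after seeing results.
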